11.1.2 Adverse Events

AE reporting is described in [Protocol Section 6](#). Volunteered, observed, and elicited AEs will be recorded in the CRF from the day the ICF is signed through 120 days after the last implant, and in a registry for the rest of each subject's life. This will include AEs subjects report spontaneously, AEs observed by the investigator, and AEs subjects report in response to open-ended questions. AEs will be coded using MedDRA® (Medical Dictionary for Regulatory Activities) version 10.1 (released by MedDRA MSCO SEP 2007) or higher. In MedDRA, each reported event is mapped to a Lowest Level Term (LLT), a Preferred Term (PT), and a System Organ Class (SOC). LLTs constitute the lowest level of terminology and can accommodate colloquial or culturally unique terms. Each LLT is linked to only one PT. A PT is a distinct descriptor for a symptom, sign, disease, diagnosis, therapeutic indication, investigation, surgical or medical procedure, or medical, social or family history characteristic; it groups together equivalent LLTs. A PT must be linked to at least one SOC but can be linked to as many SOCs as appropriate. SOCs provide the broadest level of data retrieval and comprise groupings by etiology, manifestation site, and purpose. Coding will be done by DM using a computer algorithm for exact matches or manual coding for incomplete or non-matches. All coding will be reviewed by a second member of the DM team. The Medical Monitor will review and approve the final coding prior to database lock.

A treatment-emergent AE (TEAE) will be defined as an AE that began or worsened during or after the first implantation and within 120 days after the last implantation. AEs recorded prior to the first implantation will be considered non-treatment-emergent. AEs with no recorded start date will be considered treatment-emergent, as will AEs with no recorded start time that began on the same day as the first implantation. All AEs will be listed, but only TEAEs will be summarized and analyzed.

Listings will include onset and resolution dates, study day in relationship to both first implant and most recent implant, duration (days), whether or not serious criteria apply, severity (mild, moderate, severe, life-threatening / disabling, death), action taken (none, discontinued), whether or not treatment was required, outcome (recovered, not resolved, residual effects, unknown, fatal) and relationship to study treatment (not related, remotely related, possibly related, probably related). Study day of onset in relationship to the first / most recent implantation will be calculated by subtracting the date of first / most recent implant from the AE onset date. AE duration will be calculated by subtracting AE onset date from AE resolution date. AEs that resolve on the same day will have duration = "< 1 day." Duration will not be calculated for AEs with missing or partial onset or resolution dates.

A summary of TEAEs will be provided, including incidence, severity and relationship to study treatment (implantation). TEAEs will be reported overall, as well as by SOC and PT. A summary of the most frequently reported TEAEs will also be provided, with "most frequently" defined as

occurring in at least 10% of all subjects. All TEAE summaries will be done over all implantations, as well as by implantation number.

Serious adverse events (SAEs) will also be summarized. SAEs and AEs that resulted in study discontinuation (as previously defined) will be listed separately.

Missing severity will be considered severe and missing relationship will be considered “probably related.” If the same TEAE is experienced more than once by a given subject, the TEAE will be counted only once for that subject. For summaries by severity, only the most severe TEAE per subject for each SOC and for each PT within SOCs will be tabulated. Similarly, for summaries by relationship to study treatment, only the most related TEAEs will be tabulated.

Deaths will be summarized separately, showing incidence of death overall, cancer-related death and cancer-related death by implantation number.

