6 SAFETY EVALUATIONS

6.1 Adverse Events

Adverse events mean any sign, symptom, syndrome or illness that occurs or worsens during the use of the study device/drug, regardless of causality. Symptoms of abnormal laboratory values and clinically significant asymptomatic laboratory values will constitute adverse events. A medical condition that is present when the subject enters the study is not defined as an adverse event, unless this medical condition worsens after the study drug has been administered.

The Investigator, the safety physician of The Rogosin Institute, and the Safety Data Monitoring Board will be responsible for monitoring the safety parameters that are collected in the study. As of their review of the safety/toxicity data from Phase I in June 2009, they found no adverse events attributable to the macrobeads. The Safety Data Monitoring Board will independently review all safety parameters and safety results in the study.

The description of the adverse events will use the CTCAE v3.0 definitions (issued on December 12, 2003) to define the severity or intensity of the adverse events and clinical laboratory abnormalities. The coding of the adverse events will use the most current version of the Medical Dictionary for Regulatory Agencies (MedDRA). The coding will include reported term, preferred term, and classification of the System, Organ, Class (SOC). The coding of concomitant medications will use the latest version of the WHO Drug Dictionary (WHODD).

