End of Study	When all patients have died or have been lost to follow-up, whichever occurs first
Enrolled Patients	Eligible patients who have signed an Informed Consent Form (ICF)
Sponsor	The Rogosin Institute
Time of origin (T_0)	Date of the first scan showing disease progression after completion of prior treatment. Scan must be prior to first implant. Used for mortality analyses only.
Treated Population	Patients who received at least one implant
Treatment-Emergent Adverse Event (TEAE)	An adverse event which occurred during or after the first implantation and up to 120 days after the last implantation

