6.4.1.1 Screening

Screening will occur after the ICF has been signed and within 28 days of the first implantation. Subjects will undergo all screening procedures during this time.

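### The SAP's rule for treatment-emergent AEs contradicts itself for events recorded before the first implantation that later worsen, and may leave them out of the TEAE tables

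*SAP*

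**What the plan says.** SAP 11.1.2 sets out the collection and classification of adverse events in this order:

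- Collection starts at consent: "Volunteered, observed, and elicited AEs will be recorded in the CRF from the day the ICF is signed". SAP 6.4.1.1 gives the length of the pre-implant period: "Screening will occur after the ICF has been signed and within 28 days of the first implantation".
- The definition: "A treatment-emergent AE (TEAE) will be defined as an AE that began or worsened during or after the first implantation", with an upper limit of 120 days after the last implantation.
- The sentence directly after it: "AEs recorded prior to the first implantation will be considered non-treatment-emergent".
- The consequence: "All AEs will be listed, but only TEAEs will be summarized and analyzed".

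The SAP's List of Definitions gives the term again in other words: "An adverse event which occurred during or after the first implantation and up to 120 days after the last implantation". Worsening is not mentioned there.

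Protocol 6.1, to which SAP 11.1.2 refers for AE reporting, counts worsening as an adverse event: "Adverse events mean any sign, symptom, syndrome or illness that occurs or worsens during the use of the study device/drug". It adds that a condition already present at study entry is not an AE unless it gets worse after treatment.

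**The concern.** An AE first noted in screening that becomes more severe after the first implantation satisfies both the sentence that includes it and the sentence that excludes it. The second sentence turns on when the AE was recorded and has no exception. A programmer who applies it to the AE record as first entered would flag the event as not treatment-emergent, and it would then be listed but not tabulated.

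Safety and tolerability make up the secondary objective (SAP 3.1), and the trial's estimates are meant for planning later studies (SAP 3.2). Protocol 6.7 reports intermittent fevers and intraperitoneal inflammatory reactions after implantation, so aggravation of a fever or an abdominal symptom that was already there is a relevant kind of harm. If such events are lost, the error runs in one direction only, towards lower TEAE incidence and severity.

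**Working it through.** The point is one of logic and the plan gives no figure to reproduce. The check is to take one case through each rule. The case is an AE recorded after consent and before the first implantation that rises in severity after that implantation and within 120 days of the last.

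| Rule applied | Status of the worsening | Where it appears |
|---|---|---|
| SAP 11.1.2, definition sentence | TEAE | TEAE tables |
| SAP 11.1.2, next sentence, applied to the original record | Not a TEAE | General AE listing only |
| SAP 11.1.2, next sentence, with the worsening entered as a new record after implantation | Old record not a TEAE, new record a TEAE | TEAE tables |
| SAP List of Definitions | Unclear: depends on whether a worsening counts as an event that occurred | Unclear |

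The two sentences of SAP 11.1.2 therefore collide only if the worsening stays on its original record. The next question is whether the documents say how it is recorded.

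1. **Recording.** Neither document says whether a worsening opens a new AE record or changes the grade on the old one. Protocol 6.1 makes it an adverse event but gives no data-entry rule.
2. **Fields.** The listing specification in SAP 11.1.2 has onset and resolution dates, and study day is computed from onset. No date of worsening or change of grade is mentioned.
3. **Other rules in the same paragraph.** The rules for a missing start date and a missing start time are also keyed to when the AE began.
4. **Rescue by the severity rule.** Tabulating the most severe TEAE per subject does not recover the event, because it works only on records already classed as TEAEs.
5. **Summaries by implantation.** All TEAE summaries are also to be produced by implantation number. A record with onset before the first implantation and no date of worsening cannot be assigned to an implantation. So even if the definition sentence prevails, the SAP does not say how to tabulate the event.
6. **Outputs affected on the excluding reading.** These are the TEAE tables, Table 14.3.2 (SAEs, titled as treatment-emergent), and Listings 16.2.7.3.1 and 16.2.7.3.2, which are titled the same way.
7. **Outputs not affected.** The general AE and SAE listings, the separate death summary, laboratory toxicity grades and shift tables (SAP 11.1.3), and pain scores (SAP 10.1.4.4) do not depend on TEAE status. Nor do the grade 5 stopping rule (Protocol 6.6) and the DLT definition (Protocol 6.5.1).

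**Scale per subject.** The number of affected subjects cannot be derived. What can be derived is how far one subject moves a row of a TEAE table, if that subject has no other TEAE in the row:

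- SAP 3.2 (20 colorectal, 10 pancreatic): 1/20 = 5.0 and 1/10 = 10.0 percentage points.
- Protocol Appendix 3, section 9 (74 subjects, 40 pancreatic, so 74 − 40 = 34 colorectal): 1/34 = 2.9 and 1/40 = 2.5 percentage points.

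**The case against.** The strongest reply is that the definition sentence is the operative one and expressly includes worsening, so a careful analyst would count these events.

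Protocol 6.1 also takes care of much of the problem. A symptom present at study entry is medical history, and its worsening after treatment is a new adverse event that starts after implantation, so it is a TEAE under every wording. This stands, and it narrows the case to symptoms that first arise between consent and the first implantation and then worsen.

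The List of Definitions can be read the same way. Because Protocol 6.1 builds worsening into what an adverse event is, an event that occurred after implantation may already include a worsening. This also stands: that entry is a shorter wording that needs aligning and is weak evidence by itself.

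Finally, the recording rule may exist in the CRF or the Data Management Plan, which the SAP mentions but which are not part of the protocol or SAP. That is possible. It does not remove the conflict in the SAP, which is where the TEAE flag is defined.

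A reader might infer more: that these events are certain to drop out of every AE summary, that TEAE rates are understated as a fact, or that a given share of subjects is affected. The documents do not support any of the three. The loss depends on an unstated recording rule, several safety summaries do not use the TEAE flag, and no rate of screening AEs or of their worsening is given.

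**Conclusion.** The point holds as an internal contradiction with a conditional consequence. For AEs first recorded between consent and the first implantation that later worsen, SAP 11.1.2 gives opposite answers in adjacent sentences. If the second sentence is applied to the original record, the worsening may be missing from the TEAE and treatment-emergent SAE tables, and incidence and severity would then be understated. If a worsening is entered as a new record, nothing is lost.

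The size of the effect cannot be calculated from the documents. The group concerned is limited to events arising in a screening period of at most 28 days. The primary outcome, the sample size and the stopping rule are untouched. The correction is worth making before the TEAE programs are written, because the risk runs one way and the SAP elsewhere settles doubt towards counting: an AE without a start date is treatment-emergent, missing severity is taken as severe, and a missing relationship is taken as probably related.

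**What to change.** Make three changes to the SAP.

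1. In 11.1.2, replace the sentence on AEs recorded before the first implantation with: *AEs with onset before the first implantation are non-treatment-emergent unless, at any time from the first implantation to 120 days after the last, they increase in severity (CTCAE grade, or the Protocol 6.2 scale where CTCAE does not describe the event) or become serious.*
2. Add a recording rule: *Such a worsening is entered as a new AE record, dated and graded at the worsening. The new record carries the TEAE flag and is assigned to the most recent implantation. The original record stays in the listings as non-treatment-emergent.*
3. In the List of Definitions, include worsening as well as onset, so that the entry matches 11.1.2.

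The cost is a few lines of text and one recording rule. Protocol 7.1 indicates that colorectal data have already been collected, so AE records with onset before the first implantation would need one check for later increases in severity or seriousness. TEAE counts may be slightly higher. The SAP's existing rule that a repeated TEAE counts once per subject prevents double counting.

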6.2 Classification of Adverse Events by Intensity

If the intensity of the adverse event is not described in the CTCAE v3.0, the Investigator will rate the intensity of the adverse event according to the following scale.

- Grade 1** **Mild AE.** The adverse event is transient and easily tolerated by the subject.
- Grade 2:** **Moderate AE.** The adverse event causes the subject discomfort and interrupts the subject's normal activities.
- Grade 3:** **Severe AE.** The adverse event causes considerable interference with the subject's normal activities.
- Grade 4:** **Life-threatening or Disabling AE.**
- Grade 5:** **Death**

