6.6 Premature Termination of the Study

This protocol provides for four doses of the RENCA macrobeads. The dosage to be used at each implantation will be 8 RENCA macrobeads per kg of subject body weight. The Safety Committee, as well as the investigators, will review each instance of Grade 5 adverse event. In order to protect subjects from excessive toxicities possibly associated with the study treatment, the following stopping rule will be utilized: if 3 or more subjects experience a grade 5 adverse event deemed possibly related to treatment, accrual will be halted and a thorough investigation will take place before the re-opening of accrual may be considered.

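### The default for a missing adverse-event severity has no exception for a fatal outcome, so a fatal event left blank after queries would be tabulated as severe (Grade 3) instead of death

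*SAP*

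**What the plan says.** SAP 11.1.2 gives the contents of the adverse-event listings. One item is "severity (mild, moderate, severe, life-threatening / disabling, death"; another, on the same record, is "outcome (recovered, not resolved, residual effects, unknown, fatal". Further down, the section sets the imputation rule: "Missing severity will be considered severe and missing relationship will be considered" probably related. No condition or exception is attached.

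The five severity words match the five grades of Protocol 6.2. There Grade 3 is "Severe AE. The adverse event causes considerable interference with the subject's normal activities", Grade 4 is "Life-threatening or Disabling AE" and Grade 5 is death. Protocol 6.2 applies this scale where CTCAE v3.0 does not describe the event's intensity.

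On tabulation, SAP 11.1.2 says: "For summaries by severity, only the most severe TEAE per subject for each SOC and for each PT within SOCs will be tabulated". SAP 16.2 plans two such tables: 14.3.1.3.2 (treatment-emergent events by severity) and 14.3.2 (treatment-emergent serious events by severity).

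The SAP also says: "Deaths will be summarized separately, showing incidence of death overall, cancer-related death and cancer-related death by implantation number". This is Table 14.3.1.1.2. SAP 16.1 adds Listing 16.2.7.3.2 for treatment-emergent events resulting in death. SAP 1.1 provides for queries on missing data and for computerized checks for incomplete, inconsistent or illogical values.

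**The concern.** SAP 6.3 bars imputation of missing values other than the day of a date, unless otherwise specified, so the severity rule is a deliberate exception. An imputed value should not contradict what is recorded on the same record. This one can: a record may carry a fatal outcome and an imputed severity two levels below death.

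At stake is the agreement of the safety tables with each other. The severity tables are the planned tables that break events down by term and grade. The death summary gives death overall, cancer-related death, and cancer-related death by implantation number, but the SAP plans no breakdown of it by term. A reader using the severity tables to see which kinds of event were fatal could find one shown as severe. Subjects here have Stage IV disease (SAP 3.2), so fatal outcomes will occur.

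**Working it through.** The plan gives no figure to reproduce. The check applies the stated rule to a record and follows the result into the tables.

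**Inputs**
- Severity levels in order (SAP 11.1.2, Protocol 6.2): mild = 1, moderate = 2, severe = 3, life-threatening / disabling = 4, death = 5.
- Rule (SAP 11.1.2): blank severity becomes severe.
- Tabulation (SAP 11.1.2): worst level per subject within each system organ class (SOC) and within each preferred term (PT).
- Planned sizes: 74 implanted, 40 of them pancreatic (Protocol Appendix 3, section 9), hence 74 − 40 = 34 colorectal. SAP 3.2 plans 30: 20 colorectal and 10 pancreatic.

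**Step 1. Apply the rule.** Take a record with severity blank and outcome fatal.
- The rule gives level 3.
- The outcome implies level 5.
- The imputed value is 5 − 3 = 2 levels too low.

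**Step 2. Carry it into the table.** The subject's entry for that PT (or SOC) is the maximum of 3 and the subject's recorded levels there.
- No other event above level 3: the entry is 3, where 5 is correct.
- Another event recorded at level 4: max(3, 4) = 4, where 5 is correct.
- Another event recorded at level 5: max(3, 5) = 5, so the entry is unaffected.

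**Step 3. Compare with the other outputs.** The SAP does not say which field selects records for Listing 16.2.7.3.2. If it is the outcome field, as the title suggests, the event appears there as fatal and in Tables 14.3.1.3.2 and 14.3.2 as severe.

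**Step 4. Size.** The documents give no frequency of missing severity, so the number of affected events cannot be computed. One affected subject changes a table cell by at most 1/N:

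| Planned size | All | Colorectal | Pancreatic |
|---|---|---|---|
| Protocol | 1/74 = 1.4% | 1/34 = 2.9% | 1/40 = 2.5% |
| SAP | 1/30 = 3.3% | 1/20 = 5.0% | 1/10 = 10.0% |

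These are upper bounds per affected record, not estimates of bias.

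**The case against.** The strongest reply is that such a record should seldom reach the analysis. Missing data are queried, inconsistent values are checked by algorithm, and a fatal event is a serious one that receives close attention. If a blank survived, no death would be lost, because deaths have their own summary, fatal treatment-emergent events have their own listing, and time to death is the primary efficacy outcome for colorectal subjects in the protocol and for both cancer types in the SAP. All analyses are exploratory (SAP 6.2). This stands, and it limits the point to a small one. It does not remove it: the default acts only on blanks that remain after querying, and SAP 1.1 names no check of severity against outcome.

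It can also be said that the top level, death, could not sensibly be the default for every blank. That is correct. Missing relationship goes to the top of its scale, but this does not show that severity should do the same. The defect is the missing exception for a known fatal outcome, not the choice of severe as the general default.

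A reader might infer three stronger points that the documents do not support:
- **That the accrual stopping rule is weakened.** Protocol 6.6 acts "if 3 or more subjects experience a grade 5 adverse event deemed possibly related to treatment", and has the Safety Committee and investigators review each Grade 5 event. Nothing says that it reads imputed severities from SAP tables.
- **That life-threatening events could be regraded automatically in the same way.** A life-threatening event with blank severity would also be shown as severe. However, the SAP lists only whether serious criteria apply, not which one, so the listed fields do not identify it. A query is needed.
- **That laboratory events are understated too.** SAP 11.1.3 gives toxicity grades for select parameters where applicable, and describes no link from an adverse event to a laboratory result. For a Grade 1 or 2 abnormality the default would overstate severity.

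**Conclusion.** The point holds as a minor one. Followed as written, SAP 11.1.2 places a fatal treatment-emergent event with blank severity at level 3 of 5 when its own outcome field shows level 5. That the rule reaches fatal records is an inference from the lack of an exception; the SAP does not say so outright.

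The consequence is a possible understatement of fatal events by term in Tables 14.3.1.3.2 and 14.3.2, and a possible conflict with Table 14.3.1.1.2 and Listing 16.2.7.3.2. It requires that severity is still blank after queries, that the outcome is recorded as fatal, and that the subject has no other event already recorded as death in the same SOC or PT. The effect is probably small, and its frequency is unknown. The efficacy analysis and the count of deaths are not affected.

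**What to change.** Amend the severity sentence in SAP 11.1.2 to set this order:
1. If severity is missing and the outcome is fatal, severity is set to death.
2. All other missing severities are queried to the site before database lock, including those of serious events that may have been life-threatening.
3. Only a severity still missing after that is set to severe.

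Add a footnote to Tables 14.3.1.3.2 and 14.3.2 with the number of imputed severities, split into those set to death and those set to severe.

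The cost is a short text change and a few lines of programming. Step 1 uses the outcome field that the SAP already lists, and step 2 uses the query process in SAP 1.1. No endpoint, sample size or new data item is involved.
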